## 5.2 Subject Monitoring and Management Guidelines for Certain Treatment-Emergent Adverse Events (AEs) of Interest

### 5.2.1 Fatigue and Generalized Muscle Weakness

Fatigue and generalized muscle weakness are commonly reported symptoms in patients with cancer. Both fatigue and generalized muscle weakness have been reported with sunitinib and other angiogenesis inhibitors in this class. Although the etiology of these events is generally unknown, hypothyroidism has been reported with this class of agents [Rini, 2007] and may be a contributing factor in some patients with fatigue and generalized muscle weakness.

To avoid any delay in the treatment of easily manageable conditions such as electrolyte disorders and to quickly recognize possible serious conditions such as cardiac dysfunction, the following steps are recommended when caring for subjects with fatigue and generalized muscle weakness. Subjects complaining of grade 2, 3, or 4 fatigue and/or generalized muscle weakness should be investigated as appropriate including the following suggested workup outlined below.

- Subjects with grade 3 or more fatigue and/or generalized muscle weakness should be seen immediately.
- A workup should include a detailed history and physical examination, measurement of serum electrolytes, liver function tests, an electrocardiogram, chest X-ray, thyroid function tests, and an early-morning cortisol.
- Electrolyte abnormalities should be supplemented and adrenal insufficiency or hypothyroidism should be treated with replacement therapy.
- An ACTH stimulation test should be performed if the cortisol concentration is <10 mcg/dL (280 nmol/L).
- If the subject's history or physical examination points toward symptoms or signs of congestive heart failure, the appropriate investigations should be performed including an echocardiogram.
- Subjects should be closely monitored on a weekly basis or more frequently if clinically indicated for duration of severe fatigue and generalized muscle weakness.
- Sunitinib dose (but not schedule) should be adjusted according to the dose adjustment guidelines in **Table 1: Dose Modification Algorithms for Potential Treatment-Related Adverse Events (AEs)**.

Please contact the Duke PI if you require further guidance.

### 5.2.2 Abdominal Pain

Abdominal pain is a common symptom with vascular endothelial growth factor (VEGF) receptor antagonists, including sunitinib. Bowel perforations have been reported in clinical trials of pazopanib, sunitinib, and with other agents in this class. Bowel perforations have been associated in some patients with tumor in the bowel wall, or diverticulitis, while in others there has been no clear explanation.

Although bowel perforation is a rare event, investigators and study staff at the site are advised to be vigilant of this potential complication in subjects receiving sunitinib. Please contact the Duke PI if you need further guidance or would like to discuss an event involving abdominal pain or bowel perforations.

## 5.3 Treatment Compliance

### 5.3.1 Missed Doses

Missed doses of sunitinib will be skipped, the subject should resume dosing the next day, and this should be recorded in the Pill Diary.

### 5.3.2 Concomitant Medications

All concomitant medications must be recorded on the appropriate case report form (CRF) and will be assessed at each study-related clinic visit.

### 5.3.2.1 Effects of Sunitinib on Exposure to Other Drugs

*In vitro* studies indicated that sunitinib does not induce or inhibit major cytochrome P450 (CYP) enzymes. The *in vitro* studies in human liver microsomes and hepatocytes of the activity of CYP isoforms CYP1A2, CYP2A6, CYP2B6, CYP2C8, CYP2C9, CYP2C19, CYP2D6, CYP2E1, CYP3A4/5, and CYP4A9/11 indicated that sunitinib and its primary active metabolite are unlikely to have any clinically relevant drug-drug interactions with drugs that may be metabolized by these enzymes.

See the sunitinib package insert for full details:

<http://www.labeling.pfizer.com>ShowLabeling.aspx?id=607#S7.1>

### 5.3.2.2 Drugs That May Affect Exposure to Sunitinib

#### CYP3A4 Inhibitors

Strong CYP3A4 inhibitors such as ketoconazole may increase sunitinib plasma concentrations. Selection of an alternate concomitant medication with no or minimal enzyme inhibition potential is recommended. Concurrent administration of sunitinib with the strong CYP3A4 inhibitor, ketoconazole, resulted in 49% and 51% increases in the combined (sunitinib + primary active metabolite) Cmax and AUC0-∞ values, respectively, after a single dose of sunitinib in healthy volunteers. Co-administration of sunitinib with strong inhibitors of the CYP3A4 family (e.g., ketoconazole, itraconazole, clarithromycin, atazanavir, indinavir, nefazodone, neflifinavir, ritonavir, saquinavir, telithromycin, voriconazole) may increase sunitinib concentrations. Grapefruit may also increase plasma sunitinib concentrations. **A dose reduction for sunitinib should be considered when it must be co-administered with strong CYP3A4 inhibitors.**

#### CYP3A4 Inducers

CYP3A4 inducers such as rifampin may decrease sunitinib plasma concentrations. Selection of an alternate concomitant medication with no or minimal enzyme induction potential is recommended. Concurrent administration of sunitinib with the strong CYP3A4 inducer, rifampin, resulted in a 23% and 46% reduction in the combined (sunitinib + primary active metabolite) Cmax and AUC0-∞ values, respectively, after a single dose of sunitinib in healthy volunteers. Co-administration of sunitinib with inducers of the CYP3A4 family (e.g., dexamethasone, phenytoin, carbamazepine, rifampin, rifabutin, rifapentine, phenobarbital, St. John's Wort) may decrease sunitinib concentrations. St. John's Wort may decrease sunitinib plasma concentrations unpredictably. Patients receiving sunitinib should not take St. John's Wort concomitantly. **A dose increase for sunitinib should be considered when it must be co-administered with CYP3A4 inducers.**

### 5.3.2.3 Precautions Regarding Concomitant Medications

Refer to the following links for updated lists of CYP inhibitors and inducers:

- <http://www.fda.gov/Drugs/DevelopmentApprovalProcess/DevelopmentResources/DrugInteractionsLabeling/ucm093664.htm#potency>
- <http://medicine.iupui.edu/clinpharm/ddis/table.aspx>

See also the sunitinib package insert.

<http://www.labeling.pfizer.com>ShowLabeling.aspx?id=607#S7.1>

### 5.3.3 Randomization

When the subject has been registered, has completed screening, and has been found eligible post-baseline testing, the study coordinator will request the subject's random assignment to one of the two treatment arms from the Medidata RAVE database.

For this pilot study, subjects will be randomly assigned (randomized) with equal probability to either sunitinib schedule 4/2 or 2/1. This study is open label, meaning that neither subjects nor study personnel will be blinded to treatment assignment.

**Note:** For subjects who are not eligible and fail the screening process, no further action is necessary and no additional information will be collected. However, the number of screen failures and reason for screen failure will be collected and tallied at the end of the study.

Case report forms will only be completed for those registered and randomized subjects, including those who do not receive treatment. However, subjects who do not receive the assigned treatment will be replaced and not counted toward the overall study sample size. Data limited to demographics and reason for screen failure will be collected for screen failures.

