### ***Summary: Rationale & Hypothesis***

While 4/2 is the recommended starting sunitinib dosing schedule in mRCC, retrospective evidence exists suggesting that schedule 2/1 may be at least as efficacious with an improved safety profile. However, no prospective data exists comparing the two schedules in terms of tolerability. Studies are needed to quantitate the functional cardiovascular and muscular changes induced by these two regimens. Specifically, the phenomenology of fatigue in this setting needs to be better understood. Our overall hypothesis is that schedule 2/1 of sunitinib is not only better tolerated but will be associated with less fatigue and functional cardiovascular/muscular toxicity than the 4/2 schedule. In this study, the first in a continuum of research, we will obtain data on the magnitude of VO2peak decline (mean, median, standard deviation, etc.) in each arm in order to design a more definitive study to test this hypothesis. Because future studies will include exercise training as a component, data on physiological determinants of VO2peak will be useful to design an optimal exercise training program.

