## **4 OBJECTIVES AND ENDPOINTS**

All endpoints will be evaluated at the time points specified in the Schedule of Events at the beginning of **Section 8**. See **Section 11** for Statistical Methods and Data Analysis. Key comparisons will be the change from Day 1 (week 1) to Day 85 (through week 12).

	Objective	Endpoint	Analysis
Primary	To estimate the change in VO 2 peak after 12 weeks from baseline in treatment-naïve mRCC patients treated with sunitinib on schedule 4/2 and 2/1	Change in VO 2 peak with sunitinib on schedule 4/2 or 2/1 after 12 weeks from baseline	See Section 11.1 to Section 11.4
Key Secondary	To assess the effects on the primary physiological determinants of VO 2 peak (e.g., resting and stress cardiac function and muscle function, defined as cross-sectional area,	
 
Rest and Exercise Left Ventricular Ejection Fraction (LVEF) and Cardiac Function by 2-D and 3-D echocardiography (2DE/3DE) including Global Longitudinal Strain (GLS)
 
	See Section 11.5

	Objective	Endpoint	Analysis
	strength endurance and maximal strength)	
 
Upper and lower extremity maximal muscular strength: 
 
voluntary one-repetition maximum (1-RM)
 
muscular endurance (number of repetitions to fatigue at 70% of 1-RM)
 
 
 
Muscle cross-sectional area (CSA) of the major muscles near L3 (CT scans and Slice-O-Matic® software)
 
	
Other Secondary	To evaluate changes in other measures of physical functioning/functional capacity and correlate with changes in VO 2 peak	Objective assessments (i.e., chair-stand test, timed up and go, 6-minute walk distance) of functional capacity	See Section 11.5
Other Secondary	To estimate the effects on patient-reported outcomes (i.e., fatigue and QOL)	Functional Assessment of Chronic Illness Therapy (FACIT)-Fatigue and Functional Assessment of Cancer Therapy-Kidney Symptom Index-19 (FKSI-19)- Godin Leisure Time Exercise Questionnaire	See Section 11.5
Other Secondary	To evaluate co-existent depression	Hospital Anxiety and Depression Scale (HADS)	See Section 11.5

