### 5.5 Rationale for Study Evaluations

#### PRIMARY PHYSIOLOGICAL DETERMINANTS OF VO2peak

**Rest and Exercise Left Ventricular Ejection Fraction and Cardiac Function** will be measured by 2-D and 3-D echocardiography including Global Longitudinal Strain as described previously. The rate of cardiac dysfunction was approximately 11% in a recent large randomized trial of sunitinib in which schedule 4/2 was utilized. However, to date, testing for cardiac dysfunction in clinical trials has only been performed at rest. We hypothesize that the addition of stress echocardiography will reveal other abnormalities.

**Muscle Function** will be evaluated by two outcomes: (1) upper and lower extremity maximal muscular strength will be assessed as a voluntary one-repetition maximum (1-RM) and muscular endurance (number of repetitions to fatigue at 70% of 1-RM); and (2) muscle cross-sectional area (CSA) of the major muscles near L3 will be assessed using standard of care restaging computed tomography (CT) scans and Slice-O-Matic software (TomoVision; Magog, Canada), as described previously. Standard-of-care CT scans at baseline and after 12 weeks will be used for the muscle CSA analysis. Sarcopenia, reflected as loss of muscle CSA, is known both to predict toxicity from and to develop on VEGF receptor TKI therapy. Therefore, sarcopenia may contribute to decline in cardiopulmonary function.

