#### Rest and Exercise 2-D and 3-D Echocardiography

Resting left ventricular (LV) function will be assessed by LVEF using 2-dimensional echocardiography (2DE) and 3-dimensional echocardiography (3DE), as well as by global longitudinal strain (GLS) using 2-dimensional speckle-tracking echocardiography (2D-STE) as previously described. After resting assessments, subjects will complete cardiopulmonary exercise testing as above with stress 2DE immediately post-CPET.

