#### Skeletal Muscle Function

**Muscle Cross-Sectional Area (CSA)** will be assessed using standard-of-care CT scans. Slice-O-Matic (Tomovision, Magog, QC, Canada) software will be used to measure muscle cross-sectional area and adipose tissue (subcutaneous, visceral) cross-sectional area by analysis of axial CT cross-sectional images at the time points described (see **Table 3. Schedule of Events**), as has been done previously. Average muscle and adiposity measurements will be made between 2 separate axial image cuts from each CT scan at the level of L3 by two separate reviewers who will be trained by a radiologist. The major muscles measured near L3 will include the rectus abdominis, latissimus dorsi, external and internal oblique, psoas major, erector spinae, transversospinalis, and quadratus lumborum.

**Muscle Strength** of the upper and lower body will be assessed as a one-repetition maximum (1-RM). A 1-RM is defined as the greatest resistance that can be moved through the full range of motion in a controlled manner. This dynamic strength assessment will be conducted using the following exercises:

leg press, chest press, and row. The heaviest weight lifted while adhering to the strict technique and form will be used to score the assessment. A certified exercise physiologist or trained designee will conduct this assessment in a controlled environment. Mean percentage of age and sex-predicted muscle strength will be obtained from available normative data.

**Muscular Endurance** of the upper and lower body will be assessed as the number of repetitions to fatigue at 70% of the 1-RM. The same exercises and methods will be used as in the 1-RM determination detailed above. Subjects will continue until technique, tempo, volition, or inability to complete two consecutive repetitions cause finality (per discretion of the exercise physiologist or trained designee).

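### The two reviewers who measure CT muscle area are not exempted from the open-label rule; masking the stored scans to arm and visit would remove an avoidable reading bias at little cost

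*Combined protocol and SAP*

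**What the plan says.** Section 5.3.3 (Randomization) sets the blinding rule for the whole study: "This study is open label, meaning that neither subjects nor study personnel will be blinded to treatment assignment". No class of staff is exempted there or elsewhere.

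Section 4 makes muscle CSA and the echocardiographic measures endpoints of the key secondary objective: "To assess the effects on the primary physiological determinants of VO 2 peak". On CT, Section 5.5 says: "Standard-of-care CT scans at baseline and after 12 weeks will be used for the muscle CSA analysis". Section 8.9.3 has muscle area measured on two axial cuts per scan at L3 "by two separate reviewers who will be trained by a radiologist". It fixes the vertebral level, the software and the list of muscles, and it averages the measurements. It does not say when the scans are read, or whether the reviewers know the arm, the visit or each other's result.

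On echocardiography, Section 8.9.3 says "Resting left ventricular (LV) function will be assessed by LVEF using 2-dimensional echocardiography", with 3-D imaging and strain in addition, and then "subjects will complete cardiopulmonary exercise testing as above with stress 2DE immediately post-CPET". It names no reader and says nothing about stored images or masking.

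The expected direction is stated twice. Section 3.3 expects that schedule 2/1 "will be associated with less fatigue and functional cardiovascular/muscular toxicity than the 4/2 schedule". Section 5.5 describes loss of muscle area as something known to develop on this drug class.

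**The concern.** Open-label treatment is unavoidable when two dosing schedules are compared in this way. Open-label measurement from stored images is not. Choosing a cut at L3 and outlining muscle on it leave room for judgement, and the protocol tells its staff which way the result should go.

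Two separate biases are possible. A reader who knows the visit may outline slightly less muscle at Day 85, which exaggerates the decline in both arms. A reader who knows the arm may do so more on 4/2 than on 2/1, which shifts the difference between schedules. Averaging two reviewers reduces random error but does not remove an expectation they share.

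Section 3.3 says the data on determinants of VO2peak will be used to design an exercise programme for later studies, so a distorted CSA estimate would carry forward.

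**Working it through.** The plan gives no figure for reading error or reading bias, so there is nothing of its own to reproduce here. The check compares the passages and then adds a labelled illustration.

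**Who is exposed to what**

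Inputs: 30 evaluable patients, 15 per arm (Section 11.6); CT at screening and at week 13, with CSA taken from those scans (Table 3 and its CT footnote); randomization only after baseline testing (Section 8.3 and Table 3).

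- CSA scans: 30 × 2 = 60, of which 30 are baseline and 30 are Day 85. This assumes that the evaluable patients, who are defined by VO2peak, also have both scans.
- Knowledge of visit: possible for all 60 readings.
- Knowledge of arm: possible for the 30 Day 85 readings. Baseline scans are acquired before an arm exists, so the other 30 are exposed only if they are read after randomization. The reading time is not stated.

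**How each kind of knowledge acts on the estimates**

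Write the measured change as the true change plus (reader shift at Day 85 − reader shift at baseline).

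- A shift tied to visit and equal in both arms biases each within-arm change by its full amount and cancels from the difference between arms.
- A shift tied to arm cancels from the change if it acts equally at both visits. It remains in full if it acts at Day 85 only, for example when baseline was read before randomization.

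Masking to arm alone would leave the first problem and masking to visit alone could leave the second, so both are needed.

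**Illustration of scale (assumed shifts; the documents give none)**

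Let b be the shift in units of the SD of change, with no true effect and 15 patients per arm. The standard error is 1/√15 = 0.26 SD for a within-arm mean change and √(2/15) = 0.37 SD for the difference between arms. The chance that a 5% two-sided t-test rejects comes from the noncentral t distribution, with noncentrality b√15 on 14 df within an arm and b√(15/2) on 28 df between arms.

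| Assumed shift b | Within arm (visit-related) | Between arms (arm-related) |
|---|---|---|
| 0 | 5.0% | 5.0% |
| 0.1 | 6.5% | 5.8% |
| 0.2 | 11.2% | 8.3% |
| 0.3 | 19.2% | 12.5% |
| 0.4 | 30.3% | 18.5% |
| 0.5 | 43.8% | 26.2% |

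The table shows what a test would do if one were applied to CSA. Section 11.5 plans descriptive statistics by schedule for the secondary endpoints, and CSA is not among the examples it names for the schedule models (cardiac function and muscle strength). In a descriptive report the bias is simply b.

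Masked reading changes no planned quantity: 15 evaluable patients per arm, 5% significance and 80% power for VO2peak all stay as they are.

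**The case against.** The strongest reply is that the rule in Section 5.3.3 is a general statement about treatment assignment. It does not mention image readers or visit, and Section 8.9.3 does not say that the reviewers are told the arm. Both imaging methods also refer to published descriptions that may set reading conditions. This stands in part: the documents do not order unmasked reading. What they do is declare that no study personnel are blinded, and then make no exception for outcome readers.

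The CT method already limits discretion through a fixed level, named muscles, named software and two reviewers averaged. That also stands, and it probably keeps any shift small, but it does not act on an expectation both reviewers share.

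A reader might also draw three stronger conclusions that the documents do not support:

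- **That every scan is exposed to arm bias.** Baseline scans precede randomization, so a baseline reading made at that time cannot be influenced by arm.
- **That masked echocardiography reading also needs no extra reader.** Two reviewers are planned for CT only. LVEF is an eligibility criterion (Section 7.1) and enters the cardiac toxicity rules in Table 1, so some readings must be made at once and unmasked. A masked research reading could be a second reading of about 60 studies, from loops that may not be stored.
- **That the study's main result is at risk.** VO2peak comes from gas analysis during exercise, not from image reading. Any bias from unmasked effort or test conduct is a separate matter that masked reading would not address.

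**Conclusion.** The point holds for CT muscle CSA. The plan leaves a key secondary endpoint open to knowledge of visit at both time points, and to knowledge of arm at Day 85 and at any baseline reading made after randomization, while stating the expected direction for both. The scans are stored and the reviewers already planned, so the exposure is avoidable.

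The size of the bias cannot be derived from the documents. The rejection rates above rest entirely on assumed shifts of 0.1 to 0.5 SD and are not evidence that such shifts occur. The conclusion also assumes that slice choice and outlining leave some room for judgement.

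For LVEF and strain the same reasoning applies in principle, but feasibility and cost are not documented, so the recommendation there is conditional. Overall this is a worthwhile, low-cost improvement to a secondary endpoint in a pilot. It is not a flaw in the primary analysis.

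**What to change.** 1. In Section 5.3.3, state that open label applies to patients and treating staff.
2. In Section 8.9.3, state that the baseline and Day 85 CT slices are stripped of identifiers, dates and arm, given a code, and read in random order by the same two reviewers, who are masked to arm and visit. The code key should be held by someone who does not read.
3. For LVEF and strain, apply the same masking to the research measurement where stored loops and the existing reader allow it. Eligibility and safety readings stay unmasked. If this would require a second reader, say so and decide explicitly whether it is worth doing.

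Cost for CT: de-identification, coding, and waiting to read in batches. It adds no scan, visit, patient or CT reader, and sample size, significance level and power do not change. Cost for echocardiography: unknown from the documents, and possibly a second reading of each study.

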Exploratory	To evaluate safety and tolerability of both: (a) Sunitinib and (b) Exercise testing	Eligibility rate, attrition rate, and adverse event rate (CTCAE v4.0) in each arm	See Section 11.5
Exploratory	To determine the dose intensity of sunitinib	Patient- reported drug diaries	See Section 11.5
Exploratory	To estimate early change in VO 2 peak at 4-5 weeks compared with baseline	Change in VO 2 peak from baseline to 4-5 weeks	See Section 11.5
Exploratory	To collect plasma angiome samples for analysis and correlation with primary and key secondary endpoints	Plasma angiome multiplex ELISA	See Section 11.5
Exploratory	To use real-time electronic monitoring to describe the following over the study period (subset of patients): 
 
(a) Changes in daily physical activity
 
(b) Changes in daily blood pressure
 
	
 
(a) Steps per day
 
(b) Daily blood pressure (mmHg) reading
 
	See Section 11.5

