### 8.3 Randomization

Subjects will be randomized after inclusion/exclusion criteria are met, exercise testing is complete and subject has completed an acceptable CPET and Muscular Strength. Exercise Testing Day B and Randomization may occur on the same day if eligibility is confirmed prior to randomization. Randomization and related activities can occur between days -28 to -1.

### 8.4 Treatment Period: Day 1

Day 1 is defined as the day on which the subject begins taking sunitinib.

**Note:** Subjects should start treatment with sunitinib according to the schedule to which they are randomized.

Examinations include:

- Physical Exam
- Weight, BMI
- Vital Signs
- Performance Status (KPS)
- Concomitant Medications
- Adverse Events
- CBC with Platelets (hemoglobin, hematocrit, platelet count, white blood cell count, total [absolute] neutrophils)
- Serum Chemistry (sodium, potassium, chloride, total CO2 [bicarbonate], calcium, BUN, creatinine, glucose, albumin, total bilirubin, total protein, alkaline phosphatase, AST, ALT)
- UPC (see **Appendix G**)
- Note: Many of these activities do not need to be repeated if they are performed within 14 days of day 1 (see **Schedule of Events**).
- Drug diary (give to subject)

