## 9.1 Adverse Events (AEs)

An adverse event (AE) is any untoward medical occurrence in a subject receiving study drug and that does not necessarily have a causal relationship with this treatment. For this protocol, the definition of AE also includes worsening of any pre-existing medical condition. An AE can therefore be any unfavorable and unintended or worsening sign (including an abnormal laboratory finding), symptom, or disease temporally associated with the use of sunitinib, whether or not related to use of the sunitinib. Abnormal laboratory findings without clinical significance (based on the PI's judgment) should not be recorded as AEs. **Note:** Laboratory value changes that require therapy or adjustment in prior therapy are considered adverse events.

All non-serious adverse events will be collected from the time of first dose of study drug until the End of Treatment Visit. Serious adverse events that are related to study procedures are recorded from the time the informed consent form is signed until the End of Treatment Visit (or screen failure). These AEs must be recorded in the subject's medical record and adverse events case report form.

AEs will be assessed according to the Common Terminology Criteria for Adverse Events (CTCAE), version 4.0. If CTCAE grading does not exist for an AE, the severity of the AE will be graded as mild (1), moderate (2), severe (3), life-threatening (4), or fatal (5).

Attribution of AEs will be indicated as follows:

- Definite: The AE is clearly related to the study drug or exercise testing.
- Probably: The AE is likely related to the study drug or exercise testing.
- Possible: The AE may be related to the study drug or exercise testing.
- Unlikely: The AE is doubtfully related to the study drug or exercise testing.
- Unrelated: The AE is clearly NOT related to the study drug or exercise testing.

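### Section 5.3.3 restricts case report forms to randomised subjects, while 9.1 wants procedure-related SAEs on the AE form from consent; a baseline-testing SAE in a subject never randomised is left out of the exploratory exercise-testing safety results

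*Combined protocol and SAP*

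**What the plan says.** Section 5.3.3 sets out who gets a form: "Case report forms will only be completed for those registered and randomized subjects, including those who do not receive treatment". Of screen failures it says: "Data limited to demographics and reason for screen failure will be collected for screen failures". 

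Section 9.1 takes a different line. "Serious adverse events that are related to study procedures are recorded from the time the informed consent form is signed", and the window closes at the End of Treatment Visit or at screen failure. Of the events it has just described, it says: "These AEs must be recorded in the subject's medical record and adverse events case report form". Footnote h to Table 3 repeats the collection window, but not the instruction about the form. Table 3 marks adverse events at the screening visit and at both baseline exercise-testing visits, and 8.2 lists SAEs among the data to be collected there.

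Baseline testing comes before allocation. Section 8.3 reads: "Subjects will be randomized after inclusion/exclusion criteria are met, exercise testing is complete and subject has completed an acceptable CPET and Muscular Strength". 

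Section 4 has an exploratory objective: "To evaluate safety and tolerability of both: (a) Sunitinib and (b) Exercise testing". Its endpoint includes the adverse event rate in each arm, and 11.5 displays AE rates for each arm.

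**The concern.** The maximal CPET and the one-repetition-maximum test are study procedures with their own risk. Section 9.1.2 lists arrhythmia, myocardial ischaemia, sudden cardiac death and stroke among rare but serious possibilities of the CPET. Their first use is before randomisation, so some subjects will be tested and never allocated. If one of them has a procedure-related SAE, 9.1 asks for an AE case report form and 5.3.3 does not allow one. Site staff have no rule for choosing between the two sections.

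What is at stake is the exercise-testing half of the safety objective. An event that itself keeps a subject from being randomised would also take that subject out of the tables, so any error runs towards fewer events. Section 3.3 calls the study the first in a continuum of research and says later studies will include exercise training, so these safety data have a use beyond the pilot.

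**Working it through.** The documents give no expected rate of exercise-testing events and no screen-failure count. There is therefore no figure of the plan's own to reproduce. The check is a comparison of texts, followed by an illustration.

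**Step 1: the rules applied to one subject.** Take a consented subject who starts the baseline CPET, has a procedure-related SAE, and is not randomised.

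| Source | What it requires for this subject |
|---|---|
| 9.1 and footnote h | The SAE is recorded: it falls after consent and before screen failure |
| 9.1 | It goes in the medical record and on the AE case report form |
| 5.3.3, form sentence | No case report form, because the subject is not randomised |
| 5.3.3, screen-failure data sentence | Demographics and reason for failure only |
| 9.2.1 | The SAE is reported to the DCI Safety Desk within 24 hours on a separate form |

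The second row conflicts with the third and fourth. The mention of screen failure in 9.1 and footnote h shows that subjects who are never randomised are meant to be covered.

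**Step 2: does settling Step 1 in favour of 9.1 solve it?** Not completely. Sections 4 and 11.5 plan AE rates by arm. This subject has no arm, so the event is in neither numerator nor denominator. The safety population in 11.1 is defined by having a safety evaluation and could take the subject in, but no display outside the arms is planned for it.

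**Step 3: illustration of size.** Inputs:

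- Randomised subjects, n_r = 36. This is the planned accrual in 11.6, taken here as the number randomised (assumption).
- SAEs at baseline testing among them, x_r = 0 (assumption).
- Subjects tested but not randomised, n_u = 1 to 9 (assumption; the documents give no figure).
- SAEs at baseline testing among those, x_u = 1 (assumption).

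The by-arm tables together show x_r / n_r. Counting everyone tested gives (x_r + x_u) / (n_r + n_u). Intervals are exact (Clopper-Pearson) 95%.

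| n_u | Proportion | 95% interval |
|---|---|---|
| none counted | 0/36 = 0% | 0 to 9.7% |
| 1 | 1/(36 + 1) = 1/37 = 2.7% | 0.07 to 14.2% |
| 4 | 1/(36 + 4) = 1/40 = 2.5% | 0.06 to 13.2% |
| 9 | 1/(36 + 9) = 1/45 = 2.2% | 0.06 to 11.8% |

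The intervals overlap heavily. The difference that matters is between reporting no serious event and reporting one, not the precision of a rate.

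**The case against.** The strongest reply is that the safeguards already exist. Section 9.2.1 requires SAEs to be reported within 24 hours, whether or not they are drug related, on a form separate from the case report form. The first report carries a description and causality, and follow-up gives severity, action taken and outcome. This stands: a reader might infer that the event is lost altogether, and the documents do not support that. What is missing is the event in the trial's case report form data and in its planned safety display.

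A reader might also infer that 9.1 excludes the event because collection stops at screen failure. It does not. An SAE during the test happens before the screen failure, so it is inside the window.

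The sentence in 5.3.3 that "no further action is necessary and no additional information will be collected" should not be counted as a further contradiction either. It can be read as meaning nothing more after the failure, which fits 9.1. The conflict lies in the form sentence and in the limit on screen-failure data.

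It is tempting to say that a subject with such an event would usually not be randomised. The documents do not show this. Under inclusion criterion 8 a CPET is acceptable if any one of three conditions is met, so an event at or after peak effort need not fail it. Other events would exclude, such as a myocardial infarction, which is listed in 7.2.

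Finally, the plan defines no baseline-testing rate, and 9.1 collects non-serious events only from first dose, so a complete AE rate for baseline testing was never available for anyone. That limits the claim to procedure-related SAEs. For those, 9.1 clearly intends capture, and 5.3.3 works against it.

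**Conclusion.** The contradiction is in the current text and needs no assumption: 5.3.3 and 9.1 give opposite instructions for a procedure-related SAE in a subject who is not randomised. The second gap is also textual: with AE rates planned only by arm, that event has no place in the exercise-testing safety results even if the form is completed.

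The size cannot be derived from the documents. The shift from 0/36 to between 2.7% and 2.2% rests on one assumed event, 36 randomised, no baseline-testing event among them, and 1 to 9 subjects tested but not randomised. Section 9.1.2 calls serious CPET events rare, so there may be none.

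A reader might infer that the trial will report exercise testing as safer than it was. That goes too far: it would need such an event to occur, the subject not to be randomised, and the by-arm tables to be presented as the whole experience of testing. What the documents support is that, if such an event occurs, the planned tables have no place for it, and that the omission can only lower the count.

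Severity is minor. The objective is exploratory, the trial is a pilot with 30 evaluable patients, reporting to the Safety Desk is intact, and the primary analysis is untouched.

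**What to change.** Amend 5.3.3 to agree with 9.1 and footnote h: an AE/SAE case report form is completed for any consented subject with a procedure-related SAE, randomised or not, as an exception to the limit on screen-failure data. Record how many subjects start a baseline exercise test, so that there is a denominator.

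In 11.5, report procedure-related SAEs at baseline testing pooled over all subjects who started a test, next to the planned by-arm AE rates, which stay as they are.

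The cost is a wording change, one form for a few screen failures, a count of tests started and one extra table row. Treatment, sample size and the primary analysis do not change.
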